## 9. Analysis Of Pharmacokinetics (PK)

PK parameters will be generated using Phoenix WinNonlin version 8 (Pharsight Corporation, Mountain View, California, USA).

### 9.1. PK Sampling Schedule

Blood samples for measurement of plasma concentrations of RV521 will be drawn at time points specified in the Schedule of Assessments in Section 3.10. The actual date and time (24-hour clock time) of each sampling will be recorded in the subject's source document at the site. The sampling window for each time point is identified in Table 1, Table 2, and Table 5. Deviations from planned sampling windows will be assessed before database lock for the impact on PK analyses and may be excluded from time point summaries of plasma concentrations of RV521. Actual time will be used for derivation of PK parameters.

If a subject experiences an AE Grade 3 or higher or meets SAE criteria, a blood sample for the measurement of plasma concentrations of RV521 should be collected (if less than 24 hours have elapsed since the last dose of IMP and more than 24 hours since the last PK sample), if possible. The sample will be recorded as an unscheduled time point and may be also used in PK parameters derivation using actual time.

### 9.2. Plasma PK Endpoint

The PK characteristics of RV521 to be assessed will be:  $C_{max}$ ,  $AUC_{0-12}$ ,  $AUC_{0-t}$ ,  $t_{1/2}$ ,  $AUC_{0-\infty}$ ,  $CL/F$ ,  $V/F$  and  $C_{12}$  (data permitting), and in addition for Part B: accumulation ratio, percentage fluctuation,  $AUC_{0-\tau}$ ,  $C_{ave}$ ,  $C_{min}$  ( $C_{trough}$ ) as well as any other relevant parameters.

Data regarding exposure after accumulation will be compared to parameters observed in adult subjects ( $C_{max}$ ,  $AUC_{0-\tau}$ ,  $C_{12}$  [data permitting]).

### 9.3. Presentation of Concentration Data

#### 9.3.1. Handling of Missing Data

PK concentrations before the first or single dose will be imputed as 0 to reduce the number of PK samples.

The profiles for all subjects including those with incomplete sampling profiles will be used to inform the population PK model. The results of the model will be used to simulate profiles and estimate non-compartmental parameters from the simulations. This is not considered to be an imputation of missing data and will be performed for all subjects who receive active treatment irrespective of the number of available PK samples.

#### 9.3.2. Listing and Presentation of Individual PK Data

All plasma RV521 concentration data will be listed for the PK Population. No imputed data will be included in the data listings. Individual subject linear plasma RV521 concentration-time plots will be presented on a linear scale and on a log-linear scale, using actual times relative to dose for Part A and using nominal times relative to dose for Parts B and C.

For the calculation of summary statistics, plasma RV521 concentrations that are below the limit of quantification (BLQ) will be treated as 0.

This document is confidential.

Plasma RV521 concentration data will be summarised at each nominal time point (n, number of values below BLQ [nBLQ], mean, SD, coefficient of variation (CV), minimum, median, maximum, geometric mean, and geometric CV) for the PK Population. Reporting precision for summaries of plasma RV521 concentration data will be the same as that for the PK Parameters in Section 9.4.1.

Mean  $\pm$  SD plasma RV521 concentration-time profiles will be presented on a linear scale using nominal times for the PK Population, lower SD bars will be truncated at 0.

Mean + SD plasma RV521 concentration-time profiles will be presented on a log-linear scale using nominal times for the PK Population, plasma RV521 concentrations that are BLQ will be treated as the limit of quantification value.

#### 9.4. PK Parameters Derivation

The PK parameters will be derived by non-compartmental method from estimated concentration and available observed concentration. Considering the sparse sampling the individual PK concentrations profiles will be estimated using the population PK model and post-hoc Bayesian method.

The PK parameters in Table 6 will be derived for RV521.

**Table 6. PK Parameter Determination**

Parameter	Definition	Method of Determination
$C_{max}$	Maximum observed concentration.	Observed from the PK profile
$T_{max}$	Time to reach $C_{max}$ . If the maximum value occurs at more than 1 time point, $T_{max}$ is defined as the first time point with this value.	Observed from the PK profile
$AUC_{0-t}$	Area under the plasma concentration-time curve, from time 0 to the last measurable concentration.	Linear trapezoidal method
$AUC_{0-12}$	Area under the plasma concentration-time curve, from time 0 to the 12-hour time point (using the scheduled 12-hour sampling time). $AUC_{0-12}$ will be interpolated/ extrapolated if the 12-hour concentration is not collected at the scheduled time, missing or not reportable, as appropriate.	Linear trapezoidal method

This document is confidential.

Parameter	Definition	Method of Determination
AUC 0-∞	Area under the concentration-time curve, from time 0 extrapolated to infinity.	AUC 0-t + C last /K el , where C last is the concentration at the last measurable time point.
K el	Apparent first-order terminal elimination rate constant.	Estimated by linear regression of the terminal elimination phase of the log-linear drug concentration-time curve
t 1/2	Apparent first-order terminal elimination half-life.	ln(2)/K el
CL/F	Apparent total body clearance.	Estimated as Dose/AUC 0-∞
V/F	Apparent volume of distribution.	Estimated as Dose/(K el × AUC 0-∞ )
C 12	Trough concentration at the end of 1st dosing interval	Observed from the PK profile

For Parts B and C, the PK parameters in Table 7 also be derived.

**Table 7. PK Parameter Determination – Additional Parameters for Parts B and C**

Parameter	Definition	Method of Determination
% Fluctuation	Percentage of fluctuation.	Computed as 100*(C max -C min )/C ave , where C min and C max measured over dosing interval.
T max	Time to reach C max . If the maximum value occurs at more than 1 time point, T max is defined as the first time point with this value.	Observed from the PK profile
AUC 0-tau	Area under the plasma concentration-time curve, from time 0 to the end of last dosing interval.	Linear trapezoidal method
C ave	Average plasma concentration over dosing interval.	Estimated as AUC 0-tau /tau
C trough	Plasma trough concentration	Observed from the PK profile

This document is confidential.

9.4.1. PK Parameters Summarisation

Individual subject PK parameters will be listed for the PK Population.

PK parameters will be summarised using descriptive statistics as detailed in Table 8 for the PK Population.

**Table 8. PK Parameters – Summary Statistics**

Variable	Summarised with:
AUC, C max , C ave , C min , C trough , C 12	n, arithmetic mean, SD, CV (%) calculated as 100%*SD/mean, minimum, first quartile (Q1), median, third quartile (Q3), maximum, geometric mean, and geometric CV, calculated as  Geometric CV (%) = 100%* $\sqrt{e^{z^2} - 1}$ , where z  is the variance of ln(x i )
CL/F, V/F, accumulation ratio, percentage fluctuation	n, arithmetic mean, SD, CV, minimum, Q1, median, Q3, maximum
T 1/2	n, arithmetic mean, SD, CV, minimum, median, maximum
T max	n, minimum, median, and maximum

The conventions to be used for the presentation of the descriptive statistics of PK parameters and concentrations are detailed in Table 9.

**Table 9. PK Parameters – Reporting Precision**

Statistics	Degree of Precision
Minimum, Q1, Median, Q3, Maximum	3 significant digits
Mean (arithmetic and geometric)	3 significant digits
SD	3 significant digits
CV and Geometric CV	1 decimal place

**9.5. Planned Statistical Models for PK Parameters and Concentrations**

None planned.

**9.6. Interim Analyses**

Interim PK analyses will be performed during Part A and Part B to verify if the previously developed PK model of RV521 adequately predicted the exposure in subjects ≥ 6 months to ≤ 24 months of age and subjects ≥ 1 month to < 6 months of age and report the observed exposure in the infants. The results of these PK analyses, in addition to the safety data, will guide further dosing decision by the DSMC. The PK reports to be generated are provided in the DSMC Charter.

This document is confidential.

### **9.7. Deviation from Analyses Planned in Protocol**

Currently there are no changes from the analysis planned in the protocol.

This document is confidential.

## 10. Analysis Of Pharmacodynamics (PD)

A single nasopharyngeal swab sample for the measurement of RSV viral load will be taken at each time point identified in the Schedule of Assessments for Part A (Table 1), Part B (Table 2), and Part C (Table 3) in Section 3.10. The actual date and time (24-hour clock time) of each sampling will be recorded. Deviations from planned sampling windows will be assessed before database lock for the impact on PD analyses. Actual time will be used for derivation of PD parameters. All summaries and analyses of PD data will be based on observed data in the mITT Population. Data from subjects who withdraw will be included, where possible, in all summaries and analyses.

All tables for Part C, will also be presented by the subgroups defined in Section 6.6.

### 10.1. Primary PD Endpoint and Analysis

Separate assays will be used to detect viral load of RSV A separate from RSV B by RT-qPCR. The primary analysis will report the viral load which has been quantified from either subtype, or in the case of co-infection, from the combined activity of both subtypes (total RSV viral load by RT-qPCR). The CBIA detects both RSV A and RSV B simultaneously.

If any RT-qPCR viral load result is less than the limit of detection (LoD) then a value of ½ the LoD will be used in the calculation of total RSV viral load by RT-qPCR. If any RT-qPCR viral load result falls between the LoD and the lower limit of quantification (LLoQ) then a value midway between the LoD and the LLoQ will be used in the calculation of total RSV viral load by RT-qPCR. Using these imputations, the value from each subtype will be added together at each time point to calculate total RSV viral load by RT-qPCR. This method ensures that the data collected from all subjects are consistent and not weighted to those who have both subtypes present. Total RSV viral load by RT-qPCR is calculated before any log transformations are applied.

If any CBIA viral load result is less than the LoD then a value of ½ the LoD will be used for analysis. For each assay, Table 10 shows the LoD values, LLoQ values, reported results and replacement values used for calculations:

**Table 10. LoD and LLoQ Replacement Values**

Assay	LoD	LLoQ	Reported Result (log 10 )	Replacement Value (log 10 )
RT-qPCR RSV A	2.02	2.23	<2.23	Replacement value for <LLoQ, log 10 (midway between unlogged LLoQ and LoD) = 2.14
RT-qPCR RSV A	2.02	2.23	Negative	Replacement value for <LoD, log 10 (½ of unlogged LoD) = 1.72
RT-qPCR RSV B	2.33	2.60	<2.60	Replacement value for <LLoQ, log 10 (midway between unlogged LLoQ and LoD) = 2.49
RT-qPCR RSV B	2.33	2.60	Negative	Replacement value for <LoD, log 10 (½ of unlogged LoD) = 2.03
CBIA	0.7	N/A	<0.70	Replacement value for <LoD, log 10 (½ of unlogged LoD) = 0.40

For all study Parts, log10 total RSV viral load measured in nasopharyngeal swabs by RT-qPCR in viral particles per mL, and log10 RSV viral load measured in nasopharyngeal swabs by CBIA in 50% tissue culture infective dose per mL, will be listed to 2 decimal places and summarised by nominal time point (n, mean, SD, CV, minimum, median, maximum, geometric mean, and geometric CV), including changes from baseline for post-dose measurements, for the mITT Population. All summary statistics will be presented to 2 decimal places, except CV and geometric CV, which will be presented to 1 decimal place.

This document is confidential.

Plots of the mean +/- SD observed and change from baseline values by nominal time point (baseline and each post-baseline measurement) will be presented.

For Parts B and C, log10 total RSV viral load by RT-qPCR and log10 RSV viral load by CBIA will also be summarised by nominal time point (n, mean, SD, CV, minimum, median, maximum, geometric mean, and geometric CV) and presence or absence of other known respiratory pathogens at baseline for the mITT Population. All summary statistics for viral load will be presented to 2 decimal places, except CV and geometric CV, which will be presented to 1 decimal place.

## 10.2. Secondary PD Endpoint(s) and Analyses

Secondary PD endpoints will be analysed for Study Parts B and C only. All secondary PD endpoints will be listed to 2 decimal places for the mITT Population. All summary statistics will be presented to 2 decimal places, except CV and geometric CV, which will be presented to 1 decimal place.

### 10.2.1. Area Under the RSV Viral Load Curve

The DAVG statistic will be used to summarise the change in RSV viral load from baseline over a time period, standardised to a unit of time (sometimes called time weighted average change in RSV viral load), both for total RSV viral load by RT-qPCR and for RSV viral load by CBIA.

$$\text{The statistic is calculated as: } \text{DAVG} = \frac{\sum_{i=a}^b 0.5 (Y_{i+1} + Y_i) (t_{i+1} - t_i)}{t_b - t_a}$$

Where  $Y_i$  is the change from baseline in log10 RSV viral load at time point  $i$ ,  $t$  is the actual time at the specified time point,  $a$  is the baseline assessment at Dosing Visit 1, and  $b$  is the last assessment on Follow up Day 7.

If subjects have missing viral load data post baseline, then the data that are available will be used to generate the area under the curve (AUC) and will be divided through by the corresponding time period to obtain the DAVG value. Any subjects with less than 1 viral load value post baseline will be excluded from the DAVG calculation and hence from the analysis.

If baseline viral load are missing, an imputation method will be used under the assumption that the data are missing at random. The imputed value will be determined from an ANCOVA model with baseline viral load used as the dependent factor and duration of symptoms prior to randomisation, severity of illness at randomisation and age group ( $\geq 1$  month to  $< 6$  months or  $\geq 6$  months to  $\leq 36$  months at screening) as independent factors. The predicted value for the subject with the missing baseline value will be used as the imputed value.

DAVG for total RSV viral load by RT-qPCR and for RSV viral load by CBIA will be summarised (n, arithmetic mean, SD, CV, minimum, Q1, median, Q3, maximum, geometric mean, and geometric CV) by presence or absence of other known respiratory pathogens at baseline and overall for the mITT Population.

For Part B, comparisons will be made between RV521 and placebo using a mixed effects ANCOVA model on the DAVG including a random effect term for subject, fixed effect terms for treatment group, age group ( $\geq 1$  month to  $< 6$  months or  $\geq 6$  months to  $\leq 36$  months at screening) and presence or absence of other known respiratory pathogens at baseline, and baseline RSV viral load as a covariate. The model will be fitted to the 24 subjects treated at the final doses selected for Cohort 5 (see Section 6.1).

Furthermore, the above analysis will be repeated but also including a treatment group by presence or absence of the other known respiratory pathogens at baseline interaction, in order to investigate the

This document is confidential.

treatment effect given the presence or absence of the pathogens.

For Part C, comparisons will be made between RV521 and placebo using a mixed effects ANCOVA model on the DAVG including a random effect term for subject, fixed effect terms for treatment group, presence or absence of other known respiratory pathogens at baseline, duration of symptoms prior to randomisation and severity of illness at randomisation, and baseline RSV viral load as a covariate.

For each model, a point estimate and 95% confidence interval will be calculated for the mean difference between RV521 and placebo. Estimates will also be provided separately by presence or absence of other known respiratory pathogens at baseline.

Distributional assumptions underlying the statistical analyses will be assessed by visual inspection of residual plots. Normality will be examined by normal probability plots, while homogeneity of variance will be assessed by plotting the residuals against the predicted values for the model. If the distributional assumptions of a normal distribution in the parametric approach are not satisfied, investigations into influence of outliers or non-parametric methods will be considered.

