7.2 PART C: Objectives and Endpoints

Primary Objectives for Part C	Primary Endpoint

 • Evaluate the antiviral effects of RV521, compared to placebo, on nasopharyngeal shedding of RSV in infants hospitalised with RSV LRTI 	
 • Time-weighted average change from Baseline to Day 7 in RSV viral load measured in nasopharyngeal swabs by RT-qPCR.
Secondary Objectives for Part C	Secondary Endpoints

 • To evaluate virologic parameters derived from the RSV viral load as measured in nasopharyngeal swabs • CCI [REDACTED] 	
 • Virologic parameters derived from the RSV viral load as measured in nasal swabs include but are not limited to: 
 ○ Change from baseline in viral load (RT-qPCR and CBIA) at each time point ○ Time to below viral load quantification limit (RT-qPCR and CBIA) ○ Proportion of subjects with viral load below quantification limit (RT-qPCR and CBIA) at each timepoint throughout the study • CCI [REDACTED]

 To evaluate the clinical efficacy of multiple oral doses of RV521 in infants hospitalised with RSV LRTI Evaluate the safety and tolerability of RV521 given as a multiple dose regimen 	
 Time to resolution in RSV-related symptoms Time to improvement of RSV-related symptoms Reduction in severity of symptoms by RV521, compared to placebo, measured by a composite score over time Use of supplementary oxygen, including, but not limited to, duration and maximum level of O₂ provided Time to normalisation of respiratory rate Safety of RV521 compared to placebo assessed by incidences of AEs, discontinuations due to AEs, SAEs, and clinically significant changes in laboratory tests

Exploratory Endpoints (Part C)
	
 [REDACTED] [REDACTED] [REDACTED]

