11.1.3 Pharmacodynamic Variables

Pharmacodynamic variables include individual viral loads (by RT-qPCR) and/or CBIA if available at each sampling time point, percent change from baseline for 60 and 156 hours after first dose as well as other additional PD parameters may be also considered as PD endpoints.

For Parts B and C, the DAVG statistic (time-weighted average change in RSV viral load), for both total RSV viral load by RT-qPCR and RSV viral load by CBIA, will be calculated as:

$$DAVG = \frac{\sum_{i=a}^b 0.5 (Y_i + Y_{i+1}) (t_{i+1} - t_i)}{t_b - t_a}$$

Where Y_i is the change from baseline in \log_{10} RSV viral load at time point i , t is the actual time at the specified time point, a is the baseline assessment at Dosing Visit 1, and b is the last assessment on Follow up Day 7.

Pharmacodynamic parameters, including the viral load, AUC, and any other PD parameters which are derived, will be summarised by treatment (dose level). For Parts B and C, comparisons will be made between RV521 and placebo using analysis of covariance models. Data will be log transformed as appropriate.

The primary analysis in Part C will be the time-weighted average change in nasopharyngeal RSV viral load which will be calculated from baseline (Day of Randomisation) to Day 7 and compared across treatment groups. An analysis of the RSV viral load in the presence and absence of other known respiratory pathogens will be performed. This analysis will be outlined in the SAP.

Secondary virology endpoints derived from the RSV viral load as measured in nasopharyngeal swabs will include but are not limited to:

- Change from baseline in viral load (RT-qPCR and CBIA) at each time point
- Time to below viral load quantification limit (RT-qPCR and CBIA)

- Proportion of subjects with viral load below quantification limit (RT-qPCR and CBIA) at each timepoint throughout the study

CCI [REDACTED]
[REDACTED]
[REDACTED]
[REDACTED]
[REDACTED]

Note: the key analysis will pool subjects with both RSV A and RSV B. However, selected analyses will be repeated for the RSV A and RSV B subgroups separately.

Further details of the analyses will be provided in the SAP.

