## Revision History

Version #	Date (DD-Mmm-YYYY)	Document Owner	Revision Summary
1.0	09-Oct-2020	PPD	Initial Release Version
2.0	14-Jun-2021	PPD	Clarifications and updates prior to Part A analysis

This document is confidential.

This document is confidential.

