##### Primary Endpoints for Part C

- Time to resolution of symptoms
- Time to improvement of symptoms
- Reduction in severity of symptoms by RV521, compared to placebo, measured by a composite score over time
- Use of supplemental oxygen, including, but not limited to, duration and maximum level of oxygen provided

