#### 10.2.2. Percentage Change From Baseline in RSV Viral Load

Change in  $\log_{10}$  viral load from baseline will be calculated to 60 hours and 156 hours after first dose, both for total RSV viral load by RT-qPCR and for RSV viral load by CBIA. No imputation of missing data is planned, but prior to unblinding a check will be made to determine the amount of missing data at 60 and 156 hours and whether an imputation method is warranted.

For Part B, comparisons will be made between RV521 and placebo using a mixed effects ANCOVA model on the change from baseline including a random effect term for subject, fixed effect terms for treatment group, age group ( $\geq 1$  month to  $< 6$  months or  $\geq 6$  months to  $\leq 36$  months at screening) and presence or absence of other known respiratory pathogens at baseline, and baseline RSV viral load as a covariate. The model will be fitted to the 24 subjects treated at the final doses selected for Cohort 5 (see Section 6.1).

Furthermore, the above analysis will be repeated but also including a treatment group by presence or absence of the other known respiratory pathogens at baseline interaction, in order to investigate the treatment effect given the presence or absence of the pathogens.

For Part C, comparisons will be made between RV521 and placebo using a mixed effects ANCOVA model on the change from baseline including a random effect term for subject, fixed effect terms for treatment group, presence or absence of other known respiratory pathogens at baseline, duration of symptoms prior to randomisation and severity of illness at randomisation, and baseline RSV viral load as a covariate.

For both Parts B and C the change from baseline least square mean (lsmean) estimates will be presented for  $\log_{10}$  viral load, along with the difference in lsmeans between RV521 and placebo and 95% confidence intervals. In addition the lsmean change from baseline will be back transformed and presented as a percentage change from baseline of the original viral load. Estimates will also be provided separately by presence or absence of other known respiratory pathogens at baseline.

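### SAP 10.2.1 averages a subject with no Day 7 swab over a shorter window than the Baseline-to-Day 7 average that Part C makes primary; the effect is probably small, but this rule and an indexing slip should be corrected before unblinding

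*SAP*

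**What the plan says.** - **Endpoint.** Protocol 7.2 gives the Part C primary endpoint as "Time-weighted average change from Baseline to Day 7 in RSV viral load measured in nasopharyngeal swabs by RT-qPCR". Protocol 11.1.3 repeats the window and gives the DAVG formula, in which b "is the last assessment on Follow up Day 7". SAP 10.2.1 uses the same formula and the same definition of b.
- **Missing swabs.** Under SAP 10.2.1, when post-baseline values are missing, the area from the available swabs "will be divided through by the corresponding time period to obtain the DAVG value". The entry rule is: "Any subjects with less than 1 viral load value post baseline will be excluded from the DAVG calculation". The Part C mITT definition (Protocol 11.1.1) does not ask for a Day 7 swab, and the protocol has no rule for a missing one.
- **Status of the SAP.** Version 2.0 is described as "Clarifications and updates prior to Part A analysis". Its Part C primary endpoints (SAP 4.4) are clinical, beginning with "Time to resolution of symptoms". DAVG stands under SAP 10.2: "Secondary PD endpoints will be analysed for Study Parts B and C only".
- **Missing-data check.** SAP 10.2.2 says "prior to unblinding a check will be made to determine the amount of missing data at 60 and 156 hours". This concerns the change-from-baseline analyses, not DAVG.
- **Formula.** Both documents print the sum from i = a to b over the divisor t_b - t_a. The last term then needs an assessment after Day 7.

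**The concern.** Change from baseline starts at zero. If it grows through the week, an average over 0-60 h is smaller than one over 0-156 h, and the two are then compared as if they were the same quantity. With equal missingness in the arms the treatment difference shrinks. With unequal missingness a false difference can appear, in either direction.

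The schedule allows this to happen. In Protocol Table 3a the swabs at Doses 7 to 10 are taken only in hospital. A subject sent home after Dosing Visit 3 who then misses Day 7 has a last swab at about 60-72 h. Early ending may also depend on outcome, because critical illness needing ventilatory support is a listed reason for withdrawal (Protocol 8.4.4).

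The rule was written for a secondary endpoint. The risk is that it passes unchanged into the analysis of a primary one.

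**Working it through.** **1. The plan's own figure.** Inputs from Protocol 11.2: difference 1 log10, SD 1.25, two-sided 0.05, 90% power. The t-test needs 33.8, so 34 per group (power 90.2%). Then 34 x 1.10 = 37.4, which the plan takes as 37. The sample size reproduces. The SAP rule keeps early-ending subjects in the analysis, so the comparator below is 37 per arm, with power 92.4%.

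**2. Times.** With 12-hourly dosing, Dose k falls at 12(k-1) h: Dose 6 at 60 h, Dose 7 at 72 h, Dose 10 at 108 h. Day 7 is 40-48 h after Dose 10, so 148-156 h; 156 h is used. Swabs are taken at 0, 24, 48, 60, 72, 96 and 156 h.

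**3. Share of the full-window value.** The documents give neither viral trajectories nor missingness rates, so both are assumptions. Each curve is scaled to a full-window DAVG of -1.5 (placebo) and -2.5 (RV521). The share is r = DAVG to the last swab / DAVG to 156 h. For a linear decline, r = 60/156 = 0.38.

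**4. Consequences at 37 per arm, last swab at 60 h, SD held at 1.25, noncentral t.**
- Equal missingness of 10%: effect = 0.90 + 0.10r.
- Unequal missingness, 5% v 15% (about 2 v 6 subjects), no true effect: false difference = (0.15 - 0.05) x 1.5 x (1 - r).

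| Assumed decline | r, last swab 60 h | r, last swab 96 h | Effect (10% each arm) | Power | False difference (5% v 15%) | Type I error |
|---|---|---|---|---|---|---|
| Plateau from 24 h | 0.87 | 0.95 | 0.99 | 91.8% | 0.02 | 5.1% |
| Exponential, 0.5 per day | 0.60 | 0.80 | 0.96 | 90.3% | 0.06 | 5.5% |
| Linear | 0.38 | 0.62 | 0.94 | 89.0% | 0.09 | 6.1% |
| Linear after a 24 h lag | 0.19 | 0.48 | 0.92 | 87.7% | 0.12 | 7.0% |

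At 8% v 12% the same formula, with 0.04 in place of 0.10, gives 0.01 to 0.05 log10 and a type I error of 5.0 to 5.3%.

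**5. Limits of these figures.**
- An earlier last swab is worse: at 24 h under linear decline, r = 24/156 = 0.15.
- Holding the SD at 1.25 ignores the spread added by mixing windows. Adding it as 1.25² + 0.1 x 0.9 x [m(1 - r)]², averaged over m = 1.5 and 2.5, gives SD 1.307 and power 86.2% (linear), and SD 1.346 and power 82.6% (lagged). This leaves the spread of the short-window averages at 1.25, although it would be less if it scaled with r.
- The steeper curves ask a lot of the data. Linear decline needs a Day 7 change of -5.0 in the active arm; the lagged curve needs -2.5/0.423 = -5.9. From SAP Table 10 the total-load floor is log10(10^1.72 + 10^2.03) = 2.20. Mean baselines would have to exceed about 7.2 and 8.1. The documents give no baseline loads.

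**6. Interior gaps.** If 72 h is missing but 156 h is present, the trapezoid runs from 60 to 96 h and the window is still 0-156 h.

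**7. Index slip.** Summing to b adds 0.5(Y_b + Y_{b+1})(312 - 156)/156, taking Day 14 at 312 h. With placebo at -1.5 and load flat after Day 7, linear decline gives -1.5 - 3.0 = -4.5, and the plateau gives -1.5 - 1.6 = -3.1. With b-1, numerator and divisor cover the same interval.

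**The case against.** The case for leaving this alone has substance.

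- **The SAP text predates this Part C.** It describes two arms, about 120 subjects and clinical primaries, and Protocol 11.1 provides for amendment before lock and unblinding. That stands, and it is why the point concerns what the amendment must say.
- **Few subjects should be affected.** Day 7 is a required swab, home visits are allowed (Protocol 8.2), subjects starting prohibited medication stay in follow-up (8.5.6.2), and those not completing 6 doses may be replaced (8.4.5). This supports a small expected effect.
- **A review of sampling deviations is planned.** Protocol 10.1.2.1 and SAP 6.4 assess window deviations for their impact on PD analyses before lock. Neither names missing swabs or restores the window.
- **Dividing by observed time is a known convention.** Agreed. The fault is the mismatch with the declared endpoint, not the arithmetic.
- **Imputation is not clearly better when ending depends on the unseen Day 7 value.** A simulation (1,500 trials per case, 37 per arm, between-subject SD 1.2, swab noise SD 0.5; linear decline, no effect, 5% v 15%) put the short-window bias at about +0.03 and the imputation bias at about -0.02. Where missing at random holds by construction, the figures were 0.091 and -0.004. The gain is therefore conditional, and no single recipe is compelled.

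Three stronger readings do not hold. A reader might infer that the linear case caps the damage; the lagged curve and earlier last swabs both exceed it. A reader might infer that the endpoint will be miscomputed as -3.1 to -4.5; the definition of b and the divisor make the intent clear. A reader might infer that the sample size is wrong; it reproduces and does not change.

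**Conclusion.** The mismatch is real. For a subject without a Day 7 swab, SAP 10.2.1 yields something other than the declared Part C primary endpoint, and nothing else in the documents corrects it. The distortion is probably small because such subjects should be few, but the documents supply neither curve nor missingness rate, so no bound can be given. The power range of 88-92% and the type I error range of 5.1-7.0% rest on the four assumed shapes, a last swab at 60 h, the stated missingness and an SD of 1.25. A later-starting decline, an earlier last swab or the added spread in step 5 would make matters worse.

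The index slip is editorial, but worth correcting: Part C has a Day 14 swab, so literal code would run without an error message. Overall this is a minor to should-fix item, justified by its place on the primary endpoint and the low cost of removing it.

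**What to change.** 1. Change the upper summation limit to b-1 in Protocol 11.1.3 and SAP 10.2.1.
2. In the Part C SAP amendment, make RT-qPCR DAVG primary, over one Baseline-to-Day 7 window for every subject.
3. Replace the shorter-window rule for a missing Day 7 swab with a method that estimates the full-window average, fixed before unblinding. Multiple imputation or a repeated-measures model would serve, using arm, age stratum, baseline, earlier swabs and the covariates of the final ANCOVA. State how imputed values below the assay floor are handled, and how common time points are reconciled with the actual-time rule.
4. Keep the available-data DAVG as a sensitivity analysis, and add one that departs from missing at random, such as a delta on imputed values. For scale, the swabs after 60 h carry (18 + 42 + 30)/156 = 0.577 of the trapezoid weight. With 10% missing in one arm, a delta of 1 log10 moves the difference by 0.058.
5. Report last-swab time by arm.

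The cost is a one-character correction in two documents, a paragraph in an amendment that is needed anyway, and some programming. The downside is that the primary method assumes missing at random, which is why step 4 is part of the fix.
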